### 3.5.2 Allowed Therapies

Study subjects will be allowed to take multivitamins, analgesics/antipyretics/antihistamines for local and systemic injection site reactions, and other medications as clinically indicated. Use of herbal or nutritional supplements, known to alter PSA e.g. phytoestrogens or saw palmetto is not allowed.

## 3.6 CRITERIA FOR REMOVAL FROM PROTOCOL THERAPY AND OFF STUDY CRITERIA

### 3.6.1 Criteria for removal from protocol therapy

- 3.6.1.1 Patient experiences a Grade 3 or greater toxicity attributed as possibly, probably or definitely related to vaccine as described in Section 3.3 Treatment Modifications and Immunization Stopping Rules.
- 3.6.1.2 Patient is taken off treatment by the Principal Investigator or Lead Associate Investigator for reasons other than toxicity e.g. insufficient recovery of dendritic cells to generate required vaccine dose, failure to adhere to scheduled study visits, etc.

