### **3.3 TREATMENT MODIFICATIONS AND IMMUNIZATION STOPPING RULES**

No dose modifications will be made in patients receiving vaccination. Subjects will cease to receive immunization if they experience dose-limiting toxicity (DLT). Toxicity will be graded according to NCI Common Terminology Criteria for Adverse Events (CTCAE) v3.0 ([http://ctep.info.nih.gov/reporting/ctc\\_v30.html](http://ctep.info.nih.gov/reporting/ctc_v30.html))

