#### **3.3.1 Immunization-Related Dose Limiting Toxicity (DLT)**

Immunization-related DLT is defined by the parameters outlined below attributed by the Principal Investigator or Protocol Chairperson as possibly, probably or definitely related to vaccine administration:

- 3.3.1.1 Any Grade 2 or Grade 3 or greater allergic/hypersensitivity reaction
- 3.3.1.2 Any Grade 2 or greater rash consistent with erythema multiforme.
- 3.3.1.3 Grade 3 or greater hematologic or non-hematologic toxicity, excluding lymphopenia. Abnormal laboratory studies will be repeated to verify toxicity
- 3.3.1.4 Grade 3 or greater acute vascular leak syndrome: respiratory compromise or fluids indicated.

3.3.1.5 The following Grade 3 reactions commonly associated with immunization **will** be dose-limiting:

- Injection site reactions: ulceration or necrosis that is severe; operative intervention indicated.
- Skin rash/desquamation: severe, generalized erythroderma or macular, papular or vesicular eruption; desquamation covering  $\geq 50\%$  BSA.
- Urticaria: intervention indicated for  $\geq 24$  hrs.

3.3.1.6 The following Grade 3 reactions commonly associated with immunization **will not** be dose-limiting:

- Pruritis/itching: intense or widespread and interfering with ADL lasting  $\leq 72$  hrs
- Fatigue: severe fatigue interfering with ADL lasting  $\leq 72$  hrs
- Fever:  $> 40.0^{\circ}$  C for  $\leq 24$ hrs
- Local lymphadenopathy lasting  $\leq 1$  week

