### 3.6.3 Off Study Criteria

- 3.6.3.1 Patient elects to withdraw from participation in the study at any time.
- 3.6.3.2 Patient is removed from study after resolution of Grade 3 or greater toxicities attributed as possibly, probably or definitely related to vaccine as described in Section 3.3 Treatment Modifications and Immunization Stopping Rules.
- 3.6.3.3 Patient develops evidence of brain, visceral or bony metastatic disease.
- 3.6.3.4 Patients with a calculated PSADT that has *decreased* by  $\geq 50\%$  compared to their Pre-Enrollment/Baseline PSADT. PSADT is calculated as specified in Section 3.1.
- 3.6.3.5 Patients with a calculated PSADT of  $\leq 3$  months at any of the outlined PSADT assessment time points i.e. weeks 12, 24, 36 or 48. PSADT is calculated as specified in Section 3.1.
- 3.6.3.6 For those patients receiving them, a discontinuation or dose reduction of their Flomax or 5-alpha reductase inhibitors.
- 3.6.3.7 Patient completed study

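### The Grade 3 threshold in Sections 3.6.1.1 and 3.6.3.2 does not match the dose-limiting toxicity definition in 3.3.1, so removal from vaccine and from study is unsettled for some events

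*Combined protocol and SAP*

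**What the plan says.** Section 3.3 gives the rule for the individual patient: "Subjects will cease to receive immunization if they experience dose-limiting toxicity (DLT". Section 3.3.1 defines a DLT. Two of its items begin below Grade 3: "Any Grade 2 or Grade 3 or greater allergic/hypersensitivity reaction" (3.3.1.1) and "Any Grade 2 or greater rash consistent with erythema multiforme" (3.3.1.2). The general item, 3.3.1.3, is "Grade 3 or greater hematologic or non-hematologic toxicity, excluding lymphopenia". Section 3.3.1.6 then lists exemptions under the words "The following Grade 3 reactions commonly associated with immunization will not be dose-limiting": pruritus up to 72 hours, fatigue up to 72 hours (the entry begins "Fatigue: severe fatigue interfering with ADL lasting"), fever above 40.0 °C for up to 24 hours, and local lymphadenopathy up to one week.

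Section 3.6 states removal in other terms. Under 3.6.1.1 a patient leaves protocol therapy when "Patient experiences a Grade 3 or greater toxicity attributed as possibly, probably or definitely related to vaccine". Under 3.6.3.2, "Patient is removed from study after resolution of Grade 3 or greater toxicities attributed as possibly, probably or definitely related to vaccine". Both sentences end with a cross-reference to Section 3.3 by number and title. Neither mentions DLT, a Grade 2 event or an exemption. The only other therapy-removal item, 3.6.1.2, covers non-toxicity reasons.

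**The concern.** A protocol should give one answer to whether a patient receives the next dose, and one to whether that patient stays in follow-up. Here the stopping rule runs on the DLT list and the removal rules run on a grade. Attribution is not the source of the difference, because 3.3.1 and 3.6 use the same three relatedness categories.

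The data are at stake as well as the conduct. Section 5.2.1 requires a positive assay to be confirmed at two time points, and the first assessment after vaccination starts is week 12. A patient taken off vaccine after the week 3 dose misses weeks 6, 9, 12 and 15, which is four of the five primary doses. If that patient is also off study before week 12, there is no post-vaccination immune assessment at all; if off study between weeks 12 and 18, there is only one. With nine patients per arm in the first stage, each is 1/9 = 11% of the decision. Safety is also a primary objective, so the set of patients withdrawn for toxicity should be unambiguous.

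**Working it through.** **1. The plan's own figures linked to DLT.** Section 6.2 gives one-sided 90% upper limits of 37% for 1/9 and 49% for 2/9. The exact limit is the 0.90 quantile of Beta(x+1, 9−x):

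- x = 1: Beta(2, 8) gives 36.8%.
- x = 2: Beta(3, 7) gives 49.0%.

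Both reproduce. They depend only on the counts. Section 6.2 ties the arm-level rule to DLTs as defined in 3.3.1, so the wording of 3.6 does not enter it.

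**2. The event sets side by side** (vaccine-attributed events only).

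| Event | 3.3 with 3.3.1 | 3.6.1.1 and 3.6.3.2, read literally |
|---|---|---|
| Grade 2 allergic/hypersensitivity | DLT: vaccination stops | No criterion met |
| Grade 2 erythema multiforme-type rash | DLT: vaccination stops | No criterion met |
| Grade 3 or higher lymphopenia | Not a DLT | Off therapy; off study after resolution |
| Grade 3 pruritus, ≤72 h | Not a DLT | Off therapy; off study after resolution |
| Grade 3 fatigue, ≤72 h | Not a DLT | Off therapy; off study after resolution |
| Grade 3 fever, ≤24 h | Not a DLT | Off therapy; off study after resolution |
| Grade 3 local lymphadenopathy, ≤1 week | Not a DLT | Off therapy; off study after resolution |
| Other Grade 3 or higher events | DLT: vaccination stops | Off therapy; off study after resolution |

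The DLT list is wider than the grade threshold in two classes and narrower in five.

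**3. What the cross-reference can do.** There are two plausible readings.

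- It narrows the sentence to Grade 3 or higher events that are DLTs under 3.3. The five exempt classes then drop out and the conflict for them disappears.
- It only points to the section where toxicity and stopping are discussed. All Grade 3 or higher related events then count.

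The text does not choose between these. Neither reading adds Grade 2 events to a sentence limited to Grade 3 or higher, so the first two rows remain unmatched either way.

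**4. Size, by assumption only.** The documents give no rate for the exempt events and do not say how a patient removed this way would be counted. As an illustration, suppose a fraction q of patients leaves early and is counted as non-responders, so that a 40% response rate becomes 0.40 × (1 − q). For the stated design (continue if at least 2 of 9 respond, succeed if at least 5 of 20 respond):

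power(p) = Σ over x = 2 to 9 of P(X = x) × P(Y ≥ 5 − x), with X ~ Bin(9, p) and Y ~ Bin(11, p).

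| q | p | Power |
|---|---|---|
| 0 | 0.40 | 90.2% |
| 5% | 0.38 | 87.3% |
| 10% | 0.36 | 83.8% |
| 15% | 0.34 | 79.5% |
| 20% | 0.32 | 74.5% |

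The first row agrees with the stated β = 0.10. The others show only how sensitive so small a design is to lost patients; they do not estimate what would happen.

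**The case against.** The best defence is the cross-reference. Section 3.3 contains 3.3.1, with its lymphopenia exclusion and its exemptions, so a natural reading of 3.6.1.1 is Grade 3 toxicity as that section treats it. Section 3.3.3 fits this reading, since it lets an otherwise eligible patient continue after a delay caused by toxicity. Care is given at the NIH Clinical Center, and attribution rests with the Principal Investigator or Protocol Chairperson, so practice may be consistent whatever the wording. Section 4 anticipates no significant systemic or organ toxicity. This has weight: the Grade 3 half is an ambiguity and not a flat contradiction, and the events may be rare. It does not settle the wording, and it does nothing for the two Grade 2 classes.

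Some stronger inferences are tempting, but the documents do not support them:

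- A reader might conclude that 3.6, perhaps with 3.3.3, lets a patient with a Grade 2 DLT go on being vaccinated. Section 3.3 stops vaccination without condition, and nothing in 3.6 grants permission to continue.
- A reader might conclude that the arm-level stopping rule is compromised. It counts DLTs under 3.3.1 and is untouched.
- A reader might expect more loss in the adjuvant arm. The documents give no graded rate for these events in either arm.
- A reader might require all the sections to list identical events. Stopping vaccine and leaving the study are different actions and need not share one set.

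**Conclusion.** The point holds as a wording inconsistency with practical consequences. For five event classes that 3.3.1 says are not dose-limiting, the literal text of 3.6 ends vaccination and then follow-up; whether that is intended turns on a cross-reference that can be read two ways. For two Grade 2 classes, vaccination stops under 3.3 but no removal or off-study criterion corresponds. The frequency of the conflict is unknown, and any figure for lost power rests on an assumed loss rate and on counting those patients as non-responders. No stated figure changes: the 37% and 49% limits, the sample size and the two-stage boundaries all stand. The reason to act is that the literal rule can cost doses and the two-time-point response confirmation in very small arms, and the repair is cheap.

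**What to change.** Reconcile Sections 3.3, 3.3.1, 3.6.1.1 and 3.6.3.2 in two steps. First, make 3.6.1.1 and 3.3 with 3.3.1 identify the same events for stopping vaccination, through one definition that is cited and not restated as a separate grade. Second, state separately in 3.6.3.2 which of those events also end study follow-up, and which only end vaccination. The sponsor and its safety reviewers decide which events belong in each; this review takes no position on that.

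The cost is about two sentences in an amendment, with no added patients, visits or procedures. Two side effects should be checked. If 3.6.3.2 is widened to every DLT, patients with Grade 2 DLTs would newly lose follow-up. If 3.3.1 is the section that changes, the arm-level rule would count different events. For illustration, P(at least 2 of 9) = 1 − (1−p)^9 − 9p(1−p)^8, which is 22.5% at an assumed DLT rate of 10%, 40.1% at 15% and 56.4% at 20%. Rewording only 3.6 leaves that rule as it is.

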### 3.6.2 Post Treatment Evaluation

This study is 144 Weeks in duration.

- 3.6.2.1 Clinical Evaluation: physical examination and assessment of performance status
- 3.6.2.2 Laboratory Evaluation: CBC with differential, platelets, PT/PTT, chemistries (Acute Care Panel, Mineral Panel, Hepatic Panel, total protein, CK, Uric acid, LDH), PSA.
- 3.6.2.3 Radiographic Evaluation: CXR, CT scan of the brain/chest/abdomen/pelvis, bone scan.
- 3.6.2.4 Immunologic Evaluation: CD4 and CD8 percent and absolute counts.

### 3.6.3 Off Study Criteria

- 3.6.3.1 Patient elects to withdraw from participation in the study at any time.
- 3.6.3.2 Patient is removed from study after resolution of Grade 3 or greater toxicities attributed as possibly, probably or definitely related to vaccine as described in Section 3.3 Treatment Modifications and Immunization Stopping Rules.
- 3.6.3.3 Patient develops evidence of brain, visceral or bony metastatic disease.
- 3.6.3.4 Patients with a calculated PSADT that has *decreased* by  $\geq 50\%$  compared to their Pre-Enrollment/Baseline PSADT. PSADT is calculated as specified in Section 3.1.
- 3.6.3.5 Patients with a calculated PSADT of  $\leq 3$  months at any of the outlined PSADT assessment time points i.e. weeks 12, 24, 36 or 48. PSADT is calculated as specified in Section 3.1.
- 3.6.3.6 For those patients receiving them, a discontinuation or dose reduction of their Flomax or 5-alpha reductase inhibitors.
- 3.6.3.7 Patient completed study

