#### **5.2.2.1 PSADT Response & Failure**

**(assessed in all patients at weeks 12, 24, 36, 48, 60, 72, 84, 96, 108, 120, 132, and 144.)**

- PSADT *response* is defined as:
  - a  $\geq 50\%$  increase in calculated PSADT OR

- a PSADT > 15 months
- Patient's whose PSADT is *decreased* by  $\geq 50\%$  will be considered PSADT *failures*.
- Week 24 PSADT *responders* will be allowed to receive an additional dose of TARP peptide vaccine at Week 36.

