As stated in Section 3.3.2, an early stopping rule will be used to ensure that the study subjects do not have exposure to excessive toxicity: If more than one of the first nine subjects on a given arm experiences dose limiting toxicity (defined in Section 3.3.1), enrollment will cease for that arm and revisions to the treatment will be discussed with the IRB and FDA. This is because 1/9 has an upper one-sided 90% confidence interval limit of 37%, while 2/9 has an upper one-sided 90% confidence interval limit of 49%; the former would be marginally acceptable as a rate of toxicity while the latter is not. In addition, any unusually severe toxicity noted may result in temporary suspension of accrual pending re-evaluation of the agent. All toxicities noted will be tabulated by type and grade, for each arm. Any such toxicities that appear in at least 5 patients on either arm will also have the distribution of grades of that toxicity compared between the arms using an exact Cochran-Armitage test.

The percent of patients who meet PSADT response criteria as outlined in section 5.2.2 will also be evaluated as a secondary endpoint. In addition, exploratory comparisons of PSADT among study time points will be performed as outlined in Sections 3.1 and 5.2.2. Given that there will be 6 separate comparisons of PSADT, we will only report differences with  $p < 0.01$  as being statistically significant while other differences with  $0.01 < p < 0.05$  will be considered to be trends. Appropriate 95% confidence intervals will be constructed and reported which takes into consideration the two-arm nature of the design. No formal comparison will be undertaken since the study does not have adequate power to address this comparison properly.

It is expected that 1-2 patients per month may be enrolled onto this study. Based on accrual of 18-20 patients per year, accrual should be completed in approximately 2 to 2.5 years if all 40 patients were to be required. To allow for the possibility of inevaluable patients, an accrual ceiling of 43 will be used.

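### Men whose PSADT worsens go off study, so baseline-to-later PSADT comparisons can use only men who did not fail, and the response denominator is not stated

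*Combined protocol and SAP*

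**What the plan says.** **Removal.** Section 3.6.3.4 takes a man off study when his PSADT has fallen by at least 50% "compared to their Pre-Enrollment/Baseline PSADT. PSADT is calculated as specified in Section 3.1"; it lists no assessment weeks. Section 3.6.3.5 adds a PSADT of 3 months or less "at any of the outlined PSADT assessment time points i.e. weeks 12, 24, 36 or 48". The off-study procedure (3.6.4) is a notification and a form. PSA appears under post-treatment evaluation (3.6.2), but without a schedule and without saying that it covers men who are off study.

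**Assessment.** Section 5.2.2.1 uses the same 50% fall to define PSADT failure. Response is a rise of at least 50%, or a PSADT above 15 months. Both are "assessed in all patients at weeks 12, 24, 36, 48, 60, 72, 84, 96, 108, 120, 132, and 144".

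**Analysis.** Section 6.2: "The percent of patients who meet PSADT response criteria as outlined in section 5.2.2 will also be evaluated as a secondary endpoint". Also, "exploratory comparisons of PSADT among study time points will be performed as outlined in Sections 3.1 and 5.2.2". Those sections compare baseline with weeks 12, 24, 36 and 48, week 24 with 36, and week 36 with 48. Further comparisons set baseline against weeks 60, 72 and 96, and week 48 against weeks 96, 108 and 144. Section 6.2 calls p below 0.01 significant. It gives no PSADT analysis set, no denominator and no rule for men already removed.

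**The concern.** Removal depends on the outcome being analysed, and it acts on one side only. Men whose PSADT shortens enough leave; men whose PSADT lengthens stay, and week-24 responders may receive another dose. A paired comparison at a later week needs a PSADT at that week, so it is made in a group from which the worst results have been taken out.

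The effect of vaccination on PSADT is a secondary objective (1.1.2.1). Section 6.2 also names PSADT among the outcomes to be weighed when deciding which arm goes forward. Both arms are vaccinated, so no untreated group would show how much lengthening comes from selection alone.

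**Working it through.** The plan gives no expected removal rate or PSADT response rate, so there is no figure of its own to reproduce. Its one relevant number is the maximum of 20 patients per arm (6.2).

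**1. Which comparisons are selected.** Nobody is removed for PSADT before the week-12 assessment, so baseline versus week 12 is unaffected. Every comparison that uses week 24 or later can be.

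**2. Response percentage, by arithmetic.** Take 6 responders in an arm of 20, with k men removed for PSADT failure. All men: 6/20 = 30.0%. Men remaining, 6/(20 − k):
- k = 2: 6/18 = 33.3%
- k = 4: 6/16 = 37.5%
- k = 6: 6/14 = 42.9%

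**3. Simulation with no vaccine effect.** From the documents: eligible baseline PSADT of 3-15 months, the visit schedule and both removal rules. Each PSADT is ln 2 divided by the slope of ln PSA on time. Assumed, because the documents give no values:
- five baseline PSAs;
- the SD of ln PSA (the noise);
- true PSADT, either log-uniform over 2.5-24 months or lognormal with median 8 months and log SD 0.5;
- post-entry slopes, either constant or multiplied by a random factor with log SD 0.4.

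**4. Median PSADT change, baseline to week 48** (log-uniform population, 15% noise):

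| On-study PSADT uses | Slopes | All men | Men still on study | Shift (points) |
|---|---|---|---|---|
| 12-month look-back | constant | +2.9% | +4.0% | 4.0 − 2.9 = 1.1 |
| 12-month look-back | varying | +3.4% | +11.0% | 11.0 − 3.4 = 7.6 |
| On-study values only | constant | +2.8% | +7.2% | 7.2 − 2.8 = 4.4 |

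With on-study values only and varying slopes, the shift reaches about 16 points. At 10% noise the first row falls below 1 point and the second to about 6.

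The lognormal population at 10% and 20% noise gives the same pattern:
- 12-month look-back: from +1.2% versus +1.3% to +3.5% versus +10.3%, with 90-99% of men still on study.
- Windows approximating the sequential ones in Appendix 5B: from +1.1% versus +2.1% to +2.6% versus +19.3%, with 64-87% still on study.

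**5. Comparisons that start after removals have begun** (eight lognormal scenarios). Week 48 versus 96 moved slightly downward in all eight; the largest move was from −0.3% to −2.9%. Week 24 versus 36 moved downward in five (largest from +2.0% to −4.6%), upward in two and not at all in one. Selection raises the reference value, which then regresses.

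**6. Simulated week-48 response, lognormal population.**
- 12-month look-back: 6.8% in all men versus 6.9% in men remaining (smallest gap), up to 27.0% versus 29.9% (largest). Counting removed men as non-responders over everyone enrolled gives 6.8% and 26.9%, which is almost exactly the all-men figure.
- Sequential windows, 20% noise, varying slopes: 26.2% in all men, 34.3% in men remaining, 21.9% with removed men as non-responders. With short windows the fixed denominator errs low.

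**The case against.** **The denominator.** A reader might infer that every later response percentage is computed only on men who did not fail. The text does not say that. Section 6.2 speaks of a percentage of patients, and 5.2.2.1 of all patients, which leans towards a full denominator. This stands: for the response percentage, the defect is a missing rule and a conflict with 3.6.3, not a wrong denominator.

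**The direction.** A reader might also infer that every later comparison is biased upward. Step 5 shows otherwise. Only the baseline-to-later comparisons move consistently upward.

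**The size.** Applying the removal rule to the week-3-onward windows of Appendix 5B gives about 24% off study before week 24, and a median change of +8.2% in those left versus +2.0% in all (15% noise, constant slopes). The documents do not support that as the main estimate. Section 3.6.3 refers removal to section 3.1, whose 12-month span is extended to on-study time points by 5.2.2. Appendix 5B labels its sequential windows as being for statistical analysis. The week 3-12 window also covers only nine weeks at three-week gaps, short of the minimums in 5.2.2 (3 months of values, at least 4 weeks apart). With removal on the 12-month look-back, analysis on the Appendix 5B window and constant slopes, 2.1% are off before week 24 and the medians are +2.5% versus +2.2%. By week 48, 4.6% are off: 0.046 × 20 = 0.92, under one man per arm.

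That answer assumes constant slopes. With the same mixed windows and varying slopes, the week-48 median moves from +0.5% to +4.3% at 10% noise and from +2.4% to +8.9% at 20%. The same-laboratory rule in 5.2.2 may also exclude outside PSAs from on-study calculations, which brings shorter windows back, although at week 12 these too have three-week gaps.

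**The stakes.** The time-point comparisons are exploratory, PSADT response is secondary, and the go/no-go rule is immunologic. This stands and limits the weight of the point.

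**Conclusion.** Followed as written, the plan produces a one-sided selection in the baseline-versus-week-24-and-later PSADT comparisons, and the apparent change moves upward with no vaccine effect. Comparisons starting at week 24, 36 or 48 are also selected but can move either way. The response percentage is inflated only if the men remaining are the denominator.

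At 10-15% noise the week-48 median shift runs from under 1 to about 1 point (12-month look-back, constant slopes), to about 6-8 points (same look-back, varying slopes), and to about 16 points (on-study same-laboratory values only, varying slopes). The noise, the slope variation and the PSADT distribution are assumptions, and the window is not settled by the text. The range matters more than any one figure. The primary immunologic decision is untouched.

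**What to change.** In section 6.2:

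1. Report PSADT response at each visit with all vaccinated patients in the denominator. Count a man removed for PSADT failure as a non-responder at every later visit.
2. Report the number removed for PSADT, by arm and visit, beside each PSADT comparison.
3. Reconcile 5.2.2.1 (all patients, to week 144) with 3.6.3, by stating how men already off study enter the assessment.
4. Add a supporting mixed model of log PSA on time, with random intercept and slope and a slope change after vaccination, using every pre-enrollment and on-study PSA up to removal. Because these removals depend on observed PSA, the model addresses them. It does not address the eligibility limits on baseline PSADT, which probably explain much of the small upward change seen even in all men in the simulations.

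The off-study rule itself is left as it is. The cost is a little more analysis work, no new data, and a stated response percentage that may be lower.
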